We will undertake a prospective, interventional, non-randomised, implementation study of mPOCT for COVID-19 in adults presenting to University Hospital Southampton NHS Foundation Trust. A brief validation and training phase will be followed by the post-implementation phase where patients will be recruited and tested at the point-of-care using the QIAstat-Dx Respiratory SARS-CoV-2 Panel. We will initially test patients suspected of COVID-19 based on current PHE case definitions and then progress to testing all patients with ARI as the outbreak becomes more widespread in the UK and the risks of admitting patients to hospital with unsuspected COVID-19 are high. Clinical and infection

control teams will be informed of these results in real time. The control group will consist of patients who were tested for SARS-CoV-2 by laboratory PCR but not recruited to the study during the same time period. This allows us to have a comparable control group as the outbreak progresses and hospital pathways change, as opposed to a pre-implementation group which predominantly is expected to consist of community-based patients tested in hospital for containment reasons. Only anonymised, routinely collected hospital data will be obtained for the control group. Outcome measures will be by assessed by retrospective case note analysis and will include: time to result, time in isolation facilities, detection of COVID-19 cases not initially suspected (based on current PHE case definition), antibiotic use, antiviral use, length of hospital stay, ward closures and hospital resource use. Multivariate analysis will be used to control for the effect of confounding variables between the groups.

Potential benefits to patients and the NHS

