Currently, all diagnostic testing for COVID-19 (SARS-CoV-2) in the UK is takes place in the PHE reference laboratory in Colindale, London, with testing capability being rolled out to regional PHE laboratories in late February 2020. Testing utilises RT-PCR and is thought to be highly accurate but the current diagnostic pathways are unacceptably slow; the time from sampling to results being available is currently around 3-4 days. Even when laboratory testing is rolled out to regional PHE laboratories the turnaround time for results is still likely to be too slow to allow clinical decision making in a meaningful timeframe for clinical and infection control teams. Currently there are small numbers of suspected cases of COVID-19 in the UK and the vast majority of specimens test negative. Suspected cases currently have to spend several days in hospital isolation facilities with staff using full enhanced personal protective equipment (PPE) or self-isolating at home, until results are returned. It is likely

that there will be many more suspected cases of COVID-19 over the coming weeks with high numbers of patients presenting to secondary care and therefore requiring enhanced isolation facility use and testing. In this context the additional resource demand on secondary care and laboratories will be immense and the current diagnostic pathway will be unsustainable.

The current case definition for suspected cases of COVID-19 relies on a recent history of travel to heavily affected areas in Asia and elsewhere. However as the virus is highly contagious, mainly causes mild illness and can even be transmitted by minimally symptomatic patients [5], clusters of infected patients are likely to go unrecognised as the outbreak progresses. There is therefore a high risk of COVID-19 cases that do not fulfil the case definition and so are clinically unsuspected, being hospitalised in the coming weeks. If these are not tested and appropriate isolation facilities used at presentation then widespread nosocomial transmission in hospitals is likely to occur, with devastating consequences for patients and hospitals. There is therefore a compelling argument as the outbreak spreads, for routine testing for SARS-CoV-2 in all patients presenting to hospital with compatible clinical symptoms (i.e. acute respiratory illness) alongside syndromic testing for other respiratory viruses.

Molecular POCT for respiratory viruses

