1. To assess the clinical impact of mPOCT for respiratory viruses including SARS-CoV-2 on outcomes measures including: time to test result, time in COVID-19 assessment cohort areas, time to definite ward move, length of stay in hospital, use of antibiotics, use of antivirals, ward closures, and hospital resource use, in adults hospitalised with ARI.

2. To assess the implementation feasibility of mPOCT for COVID-19.

3. To assess the ease-of-use, reliability and real-world diagnostic accuracy of the QIAstat-Dx SARS-2-CoV assay, , using respiratory samples prospectively collected from adults presenting to hospital with ARI, compared to the reference standard of PHE laboratory RT-PCR for SARS-CoV-2.

6. Recruitment and Study Processes

Overview

This is a non-randomised, controlled, implementation study of mPOCT for respiratory viruses including COVID-19 with prospective recruitment for participants in the intervention phase. The intervention consists of testing respiratory samples from patients at the point-of-care using the QIAstat-Dx Respiratory SARS-CoV-2 Panel. In the contemporaneous control group, routinely collected data on outcomes in patients tested for COVID-19 using laboratory RT-PCR, including time to test result. In the intervention phase patients will be tested using the QIAstat-Dx Respiratory SARS-CoV-2 Panel with results delivered immediately to the clinical and infection control team and outcome and diagnostic accuracy data collected retrospectively. A brief validation phase will precede the intervention phase. Study processes that patient-participants undergo in intervention phase are summarised in Figure 1.

[figure not shown]

Figure 1: Participant flow through the study

POCT = point-of care test

*if lacks capacity to consent, participant's consultee may be substituted here

Control group

Patients (≥18 years old) presenting to hospital with ARI who have been tested for SARS-CoV-2 during the same time period as part of standard clinical care (but not included in the intervention) via University Hospital Southampton NHS Foundation Trust (UHS) will be identified via (laboratory) information management system and select clinical data will be obtained by electronic records including age, sex, co-morbidity, observations, blood test results, length of hospital stay, and time to test result. Consent is not obtained for these patients, and only anonymised data already collected as part of routine clinical care will be used.

Screening

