Participants will be enrolled and assigned a unique participant identification number consecutively. Respiratory samples will be collected from patients by an appropriately trained member of research staff wearing full PPE as defined by UHS infection prevention and control policy. A combined nose and throat swab, and if available, a lower respiratory tract sample (sputum, or for patients in critical care units BAL or ET secretions) will be obtained and tested. Samples will be immediately placed in a sigma MWMM (molecular medium) or similar tube (containing detergent and Guanidine thiocyanate) to rapidly and completely inactivate any virus present (within 1 minute). The sample will then be loaded in the test kit and tested on the QIAstat-Dx analyser housed in the acute area. The result will be available in around 1 hour and will be delivered to the clinical and infection control teams as soon as results are available. The system will be de-contaminated prior to and after use in accordance with the manufactures instructions.

All participants may be approached for a finger-prick blood test with the FebriDx (RPS, FI., USA) and a second nose and throat swab in viral transport media (participants may opt out of one or both of these).

Patients testing positive for COVID-19 and for 'seasonal' non-COVID-19 coronaviruses may be approached for additional respiratory samples and/or blood samples for additional virological, serological and host response analysis at various time points (see Table 1 and laboratory analysis plan).

Participant involvement end date

Participant involvement in the study is considered ended once their last physical interaction with the research team has finished, although some retrospectively collected outcome measures will still be collected from records after this time (e.g. 30 and 60 day mortality). For patients testing negative for coronaviruses this is expected to be the same day as enrolment. For patients testing positive for a coronavirus, this may be the same day as enrolment if no further samples are collected, or the date of the last additional samples acquired (see Table 1). Participant withdrawal is discussed separately.

Day 0 (enrolment day) +/- 72 hours	Day 14 (+/- 4 days)	Day 28 (+/- 4 days)
Blood test (max 22ml)	Blood test (max 22ml)	Blood test (max 22ml)
Additional nose & throat swabs +/- lower respiratory sample	Nose & throat swabs	Nose & throat swabs

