Table 1. Optional additional tests for those testing positive for SARS-CoV-2 or any endemic coronavirus

Inclusion / exclusion criteria

Inclusion criteria:

- Is a patient in ED, AMU, HDU, GICU, medical wards, or another location within Southampton General Hospital, University Hospital Southampton NHS Foundation Trust (UHS)

- Aged ≥18 years old

- Can be recruited to the study within 24 hours of presentation to hospital

Plus:

- Has acute respiratory illness (ARI)*

OR

- Does not have ARI but is a suspected case of COVID-19 according to the current PHE case definition OR

- Does not have ARI or fulfil the PHE case definition of a suspected case but testing for SARS-CoV-2 is considered necessary by the responsible clinical team

*An episode of acute respiratory illness is defined as an acute upper or lower respiratory illness (including rhinitis, rhino-sinusitis, pharyngitis, pneumonia, bronchitis and influenza-like illness) or an acute exacerbation of a chronic respiratory illness (including exacerbation of COPD, asthma or bronchiectasis). For the study, acute respiratory illness as a provisional, working, differential or confirmed diagnosis must be made by a treating clinician.

Exclusion criteria:

- Not fulfilling all the inclusion criteria

- Declines nasal / pharyngeal swabbing

- Consent declined or consultee consent declined
- Already recruited to the study in the last 14 days

Further inclusion / exclusion notes

Concurrent, prior, or subsequent enrolment in another study is not necessarily an exclusion criterion; this is at the discretion of the chief investigator and will be assessed on a case-by-case basis. Local R&D measures including a "12 week exemption form" must be in place and agreed with the chief investigator that may facilitate co-enrolment in other studies.

The inclusion of pregnant women is permitted in the study. No additional risk is perceived to pregnant women or their offspring by any of the study procedures. No additional data collection or monitoring is therefore anticipated in this group. It may be especially important to include pregnant women in COVID-19 research, as infection with influenza is associated with worse outcomes in pregnancy [11]. Data on abnormalities at birth or congenital defects and other serious adverse events are collected and may be reportable (see relevant section on Safety).

Staff testing

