Non-hospitalised hospital staff members may be included in the intervention phase of the study, if they satisfy the other inclusion & exclusion criteria. The same consent and study procedure processes are followed. However, their results will not be included in analyses of most outcome measures, with the exception of time to result. Days away from work may be used as an additional outcome measure.

Participant Withdrawal

A participant, or their consultee where a participant lacks capacity, may decide to withdraw from the study at any time, without giving reason, and with no detriment to their medical care or legal rights.

The chief investigator may withdraw a patient from the study in the interests of participant safety or the integrity of the research study, or on the advice of the sponsor's representative (R&D department).

Any patient, or their consultee where a patient lacks capacity, who is withdrawing from the study has the options withdraw and have data and/or samples collected so far retained, or withdraw and have their data and/or samples destroyed (but signed consultee declaration forms, minimal personal identifiable information to record the withdrawal, and any completed point-of-care test result will be retained). Although the study procedures are very brief, if a patient loses capacity after enrolment but before the study procedures are completed, consultee consent must be sought to continue with any study procedures, or the participant must be withdrawn.

A note to file would normally be sufficient to record any withdrawal.

7. Outcomes

Primary outcome

• The primary outcome measure is the time from COVID-19 test being requested to the result being available to clinical teams.

Secondary Outcomes

- The time from presentation to hospital to COVID-19 test result
- Time spent in COVID-19 assessment cohort area
- Time to definitive ward move
- Number of bed moves •
- Duration of hospitalisation •
- Number and proportion of clinically unsuspected COVID-19 positive patients detected •
- Proportion of patients treated with antibiotics
- Proportion of patients treated with single doses or brief courses (<48 hours) of antibiotics •
- Duration of antibiotic use, days
- Proportion of all influenza antiviral use occurring in influenza positive patients •
- Proportion of all influenza antiviral use occurring in influenza negative patients •
- Time from admission to influenza antiviral commencement

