Accepting that the prevalence of COVID-19 during the study is highly speculative at present, and so formal samples size calculation for diagnostic accuracy studies are not possible, testing 500 patients will allow us to make an ongoing assessment of the real-world diagnostic accuracy of the QIAstat-Dx Respiratory SARS-CoV-2assay compared to the current reference standard of laboratory PCR testing using the PHE RdRP assay.

The control group will be 500 patients for an adequate comparison.

9. Data collection

Demographic and clinical data will be collected for all patients at enrolment including: age, sex, ethnicity, smoking status, vaccination status, co-morbidities, medication use, symptoms, duration of illness prior to hospitalisation, observations (pulse rate, respiratory rate, blood pressure, oxygenation status), laboratory results, radiology results, antimicrobial and antiviral use prior to hospitalisation and provisional diagnosis. Data will be recorded on a Case Report Form, which we intend to be electronic (ALEA). Once patients have been discharged or after 30 days (whichever is soonest), clinical data will be collected retrospectively from electronic and physical case notes including: use of antivirals, duration of antivirals, time from assessment to antiviral use, use of side room facilities, time from assessment to isolation facility use, time to clinical stability, duration of supplementary oxygen use, duration of hospitalisation, complications including ICU and RHDU admission, representation and readmission to hospital within 30 days, final diagnosis and mortality. The number of diagnostic tests and procedures performed will also be recorded and data will also be collected on the turnaround time of respiratory virus test results in each group.

10. Data Management

The subjects' anonymity will be maintained. The study team will keep a log of each subject's name, hospital ID number, date of birth, and unique participant trial number. The participant details will be recorded on the secure NHS Edge system in a similar manner, including NHS number. This participant trial number is used on documents after screening to maintain confidentiality. Documents that are not anonymous (e.g. signed informed consent forms) will be maintained separately, in strict confidence.

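### Whether a COVID-19 case was clinically unsuspected is read from case notes after the result is known, and for patients with ARI no listed item fixes it beforehand, so the count can be wrong in either direction

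*Protocol*

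**What the plan says.** The outcome appears in Section 7 as "Number and proportion of clinically unsuspected COVID-19 positive patients detected". That section gives no definition, time point or assessor. The Methods in Section 2 give both the method and the yardstick. The sentence begins "Outcome measures will be by assessed by retrospective case note analysis and will include", and its list contains "detection of COVID-19 cases not initially suspected (based on current PHE case definition".

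Three places fix the timing:

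- The overview in Section 6 has "outcome and diagnostic accuracy data collected retrospectively".
- Section 9 dates the review: "Once patients have been discharged or after 30 days (whichever is soonest), clinical data will be collected retrospectively from electronic and physical case notes".
- The procedures in Section 6 say of the point-of-care test "The result will be available in around 1 hour", with the result passed to the clinical team at once.

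On what decides suspected status, the Introduction (Diagnosis of COVID-19) says "The current case definition for suspected cases of COVID-19 relies on a recent history of travel". The eligibility criteria use the definition as an entry route only for those without ARI: "Does not have ARI but is a suspected case of COVID-19 according to the current PHE case definition".

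**The concern.** Length of stay and time to result can be read from timestamps. This outcome instead turns on what was known about a patient before the result. If that is reconstructed weeks later from a record that already holds the positive result, two things can go wrong. The deciding history may never have been written down, or it may have been asked for and written down only because the test was positive.

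The count bears on one of the protocol's stated expectations, that finding unsuspected cases at the door will limit spread within the hospital and ward closures (Sections 2 and 4). A count that depends on how full the notes are is weak evidence for that.

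**Working it through.** The protocol gives no expected number of unsuspected cases and calls prevalence highly speculative (Section 8), so there is no figure to reproduce. The check is mainly a reading of the passages together.

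1. **Order of events.** The result comes at about 1 hour (Section 6), the note review at discharge or 30 days (Section 9). The result is in the record when the notes are read. The outcome counts only positive patients (Section 7), so the task is to classify patients who have tested positive.

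2. **What eligibility settles.** A patient without ARI enters either because the PHE definition is met or because it is not met but the clinical team wants a test. Status must therefore be settled at entry for these patients. A patient with ARI enters whether or not the definition is met, so eligibility is silent for them.

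3. **What staged recruitment settles.** Section 2 describes a first stage confined to patients meeting the definition. Their status is known, but by construction none of them is unsuspected. The unsuspected cases with ARI must come from the wider recruitment, where status is not fixed.

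4. **What the enrolment data settle.** Section 9 lists symptoms, duration of illness, observations, radiology and provisional diagnosis, among others. It does not list travel or contact history, or case-definition status. The items collected later include side-room use and time to isolation. Those help, but in the intervention group the result arrives so quickly that isolation may follow the result and not the suspicion.

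5. **Direction of error.** Let P be the positives, U the truly unsuspected, m the share of suspected cases whose qualifying history is missing from the notes, and f the share of unsuspected cases moved to suspected by history recorded after the result. Then

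   observed count = U + m(P − U) − fU.

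   Illustration with assumed inputs only: 10% of 500 tested positive gives P = 50; U = 10 (20% of positives); P − U = 40.

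   - m = 5%, f = 0: 10 + 2 = 12 (24%)
   - m = 10%, f = 0: 10 + 4 = 14 (28%)
   - m = 20%, f = 0: 10 + 8 = 18 (36%)
   - m = 0, f = 20%: 10 − 2 = 8 (16%)
   - m = 5%, f = 20%: 10 + 2 − 2 = 10 (20%)

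   The sign depends on whether m(P − U) exceeds fU. The documents give none of the four quantities. The last line shows that the two errors can also cancel in the total while individual patients are misclassified.

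6. **Controls.** The control-group paragraph in Section 6 limits these patients to anonymised data already collected in routine care. Its listed items include neither presenting history nor suspected status, so a field completed by study staff before the result cannot be obtained for them.

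**The case against.** The strongest reply is that the argument rests on an open list. Section 9 says enrolment data include certain items, the case report form is not shown, and a single yes/no item is the sort of detail a protocol may leave to the form. There are also other traces from before the result: provisional diagnosis bears directly on clinical suspicion, and a patient treated as suspected would usually have been isolated. The word initially points to the time of presentation, and in the eligibility criteria the current definition can only mean the one in force at recruitment. Finally, this is one of many secondary outcomes.

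Much of this stands. The protocol does not contradict itself here, a partial record from the time does exist, and the importance is limited. It does not remove the point, because the protocol states how the outcome will be assessed, and that is by reading notes afterwards. A later analysis plan cannot recover a history that nobody recorded before the result.

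A reader might go further and infer the following, which the documents do not support:

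- **That the count will be inflated.** Missing history raises it, but history recorded after a positive result lowers it.
- **That the protocol has the classification made by staff who know the result.** It does not say who classifies or what they see. Knowledge of the result is a strong inference from the timing, and no masking is described.
- **That a missing travel entry will be read as definition not met.** No such rule is stated.
- **That travel history governs throughout.** The Introduction describes the definition at the time of writing, and it may change during up to 6 months of recruitment.

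**Conclusion.** The point holds as a weakness of ascertainment in one secondary outcome. For intervention patients with ARI, nothing the protocol lists commits staff to recording, before the result, whether the PHE definition in force was met, and the stated method is retrospective note review. The count is therefore open to misclassification in either direction.

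Its size cannot be derived from the documents. The illustrative range of 8 to 18 against a true 10 rests wholly on assumed prevalence, case mix and completeness of notes, and should not be cited as an estimate of bias. The primary outcome in Section 7, time from request to result, is unaffected.

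The conclusion assumes that the case report form holds no pre-result field for case-definition status beyond what Section 9 lists. If it does, only the wording of the Methods needs correcting. The change is worth making because it is nearly free and the information cannot be recreated later.

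**What to change.** For every intervention-group participant, record on the enrolment case report form, before the mPOCT result is read, whether the PHE case definition in force that day is met (yes/no, with the date). State in Section 7 that the intervention-group outcome is derived from this field, and take it out of the list in the Section 2 Methods that is assessed from case notes. Dating the entry also settles which version of the definition applies.

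Report the outcome as an intervention-group measure. If a control-group figure is given, flag it as note-derived. The same flag is needed for any intervention participant enrolled before the field exists; the safety update in Section 12 shows that recruitment was under way by 3 June 2020.

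The cost is one extra item on a form already completed at enrolment. The downside is that the two groups are not ascertained in the same way, so a between-group comparison of this outcome should not be relied on.

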We hypothesise that the use of a routine mPOCT for respiratory viruses including SARS-CoV-2 in adults presenting to hospital with suspected COVID-19 and/or ARI will dramatically reduce the time from patient presentation to results, compared to the current standard of PHE laboratory RT-PCR. We expect that timely detection or exclusion of COVID-19 will lead to improvements in early directed isolation facility and enhanced PPE use or de-isolation/de-escalation, in addition to other potential benefits such as reduced length of stay, improved use of antibiotics and antivirals and resource use and cost for the NHS. The detection of COVID-19 positive cases presenting to hospital and not initially suspected based on current the PHE case definition will prevent widespread nosocomial transmission of SARS-CoV-2 and associated hospital ward closures.

3. Abbreviations and Definitions

AE: Adverse Event AMU: Acute medical unit ARI: Acute respiratory illness CES: School of Clinical and Experimental Sciences, Faculty of Medicine University of Southampton **CI:** Chief Investigator COVID-19: Coronavirus disease 2019 CRF: Case Report Form ED: Emergency Department GICU: General Intensive Care Unit HRA: Health Research Agency ICU: Intensive care unit mPOCT: Molecular Point-of-Care test PCR: Polymerase Chain Reaction PHE: Public Health England PI: Principal Investigator POCT: Point-of-Care Test **PPE: Personal Protective Equipment REC: Regional Ethics Committee** RHDU: Respiratory High Dependency Unit RT-PCR: Reverse Transcriptase Polymerase Chain Reaction SAE: Serious Adverse Event

SARS-CoV-2: Severe acute respiratory syndrome coronavirus 2

UHS: University Hospital Southampton NHS Foundation Trust

WHO: World Health Organisation

4. Introduction

COVID-19

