The clinical teams in the various areas shall identify potentially eligible patients in the clinical areas by regularly reviewing the admitted patients and electronic admission systems against eligibility criteria and informing the research team. Many members of the research team are healthcare professionals who are looking after these patients directly. The initial approach to potential participants will be made by clinical team members and not by additional research staff.

Consent

The study team will obtain written informed consent for those fulfilling eligibility criteria and willing to be recruited for those with capacity, or assent via consultee for those without capacity, using the dedicated study forms. As noted above, in view of the acute nature of patients' illnesses, the potential benefits of rapid identification of viruses including SARS-CoV-2, the usual 24 hour consideration period for a participant or consultee will not apply.

Discussion of the study will be provided to patients, or their consultee for those lacking capacity, by study staff. This includes supply of a participant information sheet for the participant or witness to read and retain.

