Summaries of all baseline characteristics will be presented using means and standard deviations, medians and interquartile ranges, or frequencies and percentages, as appropriate. The groups will be compared using chi-square tests for equality of proportions for binary data (e.g. proportion of cases of influenza detected) and using independent-samples t-tests or non-parametric equivalent as appropriate for continuous data (e.g. duration of isolation facility use, etc.).

The primary outcome measure (median duration of isolation facility use) will be compared between the groups using the Mann-Whitney U test. Multivariate analysis will be performed to adjust for confounding variable in view of the non-randomised nature of the study.

12. Safety

Serious Adverse Events

The risks of respiratory tract sampling and additional blood tests being taken are minimal and where occurring are likely to be mild. No additional adverse events related to mPOCT for respiratory viruses including COVID-19 are anticipated. However active monitoring and reporting of severe adverse events will be undertaken. A Serious Adverse Event (SAE) is any adverse event that:

- Results in death

- Is life-threatening

- Requires hospitalisation or prolongation of existing hospitalisation

- Results in persistent or significant disability or incapacity
- Consists of a congenital anomaly or birth defect

In the event of a SAE, a study doctor will consider the likelihood of the event being related to the study based on the documented evidence from the treating clinicians. SAEs will be reported via the sponsor's standard forms and processes. SAEs will be reported within 24 hours of the study team learning of the SAE. In the event of a SAE, the PI will be involved in deciding whether this was a study-related event. In the event of a study-related SAE, the REC will be informed as per HRA regulations.

Participants already admitted to AMU, or another hospital ward including high dependency or an intensive care unit, or are in ED but with a decision already made to admit, are considered already hospitalised. However, an adverse event leading to prolongation of their existing hospitalisation will be counted as an SAE.

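### The primary clock starts at a test request, an event the point-of-care pathway does not contain, so the groups may be timed from different points and the primary difference may be overstated

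*Protocol*

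**What the plan says.** Section 7 (Primary outcome) sets the primary measure as the "time from COVID-19 test being requested to the result being available to clinical teams". It does not say what counts as the request in either group.

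Section 6 sets out the route to an mPOCT result:

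- Under Screening, clinical teams find patients by "regularly reviewing the admitted patients and electronic admission systems against eligibility criteria and informing the research team".
- Under Consent, "The study team will obtain written informed consent for those fulfilling eligibility criteria", or a consultee gives assent.
- Under Procedures, research staff take the swab and run it on the analyser.
- Under Intervention phase, every patient with acute respiratory illness is to be approached, so the trigger is eligibility and not an order.
- The inclusion criteria add "Can be recruited to the study within 24 hours of presentation to hospital".

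Controls (Section 6, Control group) had a SARS-CoV-2 test as part of ordinary care, are found through the laboratory system, and have no study consent step.

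Two other places bear on the clock. Section 2 (Potential benefits) predicts that mPOCT will "dramatically reduce the time from patient presentation to results", and Section 7 lists "The time from presentation to hospital to COVID-19 test result" only as a secondary outcome. Section 11 states: "The primary outcome measure (median duration of isolation facility use) will be compared between the groups using the Mann-Whitney U test".

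**The concern.** A request is a natural, recordable event for a laboratory test ordered in routine care. It does not appear among the steps that lead to an mPOCT result. Someone extracting data for an mPOCT patient must therefore choose a start: the clinician's decision, the referral to the research team, enrolment, the swab, or a parallel laboratory order if there is one. These can be hours apart.

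If enrolment or swab is chosen, the time spent finding, approaching and consenting the patient is left out, and with a swab start so is the wait for the swab. The control clock, starting at the order, still counts its own wait for a swab. The asymmetry would favour mPOCT.

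Section 2 (Methods) says outcomes are assessed by retrospective case note review, so this choice could be made after the event by people who know the group. Section 11 cannot settle it, because it attaches the primary label to a different variable. Implementation feasibility is a stated aim, so the time needed to reach patients is part of what the study sets out to measure.

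**Working it through.** The protocol has no planned effect on the primary outcome to reproduce. Section 8 sets 500 per group on kit supply; the only sum to check is 500 + 500 = 1000, which agrees with the Synopsis.

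**Inputs**

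- m, mPOCT time: about 1 h (Section 6, Procedures); under 2 h in earlier trials (Section 4). Used: 1 and 2 h.
- L, laboratory time: 1 to 2 days in earlier trials (Section 4, Molecular POCT); about 3 to 4 days from sampling when the protocol was written (Section 4, Diagnosis). Used: 24, 48, 72 and 96 h.
- d, mPOCT pathway time left out if the clock starts at enrolment or swab. Not given. Assumed: 0 to 24 h, the top being the limit from presentation to recruitment.
- c, control time from presentation to laboratory request. Not given. Assumed: 0 to 24 h.

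**Step 1. Clock that counts the identification and consent time**

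Apparent gain = L − m. Gain with the omitted time counted = L − (m + d). The overstatement is d hours, or d / (L − m) of the apparent gain.

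Gain in hours, m = 1 h (for m = 2 h subtract one hour throughout):

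| L | d = 0 | d = 2 | d = 6 | d = 12 | d = 24 |
|---|---|---|---|---|---|
| 24 h | 23 | 21 | 17 | 11 | −1 |
| 48 h | 47 | 45 | 41 | 35 | 23 |
| 72 h | 71 | 69 | 65 | 59 | 47 |
| 96 h | 95 | 93 | 89 | 83 | 71 |

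Share of the apparent gain, from L = 96 h, m = 1 h to L = 24 h, m = 2 h:

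- d = 2 h: 2/95 = 2% to 2/22 = 9%
- d = 6 h: 6/95 = 6% to 6/22 = 27%
- d = 12 h: 12/95 = 13% to 12/22 = 55%
- d = 24 h: 24/95 = 25% to 24/22 = 109%

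The sign changes only when d > L − m. For L = 24 h that needs d above 22 to 23 h. For L = 48 h it needs d above 46 h, outside the assumed range.

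**Step 2. Presentation clock**

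Here d is the whole interval from presentation to the recorded mPOCT start. A request clock also drops c from the control group, so the net bias against a presentation clock is d − c. For d = 6 h this is +6 h at c = 0, 0 h at c = 6 h and −6 h at c = 12 h.

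**Step 3. If the start is a clinical event**

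If the mPOCT start is recorded as the clinician's decision, the referral or a parallel laboratory order, identification and consent time from that event on is counted. Then d = 0 in Step 1 and the asymmetry disappears.

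**The case against.** A reader might infer that the primary effect is overstated, that up to 24 hours of screening and consent is removed, and that this happens in one group only. The protocol does not support that reading, for these reasons:

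- It never says that the mPOCT clock starts at enrolment or swab. Referral to the research team works much like a request and comes before consent. One eligibility route rests on the treating team judging a test to be needed. How a timestamp is captured may be settled in a CRF or SAP that is not shown.
- The 24 hours caps the whole interval from presentation to recruitment, including arrival and clinical assessment, which controls also undergo. It is not a consent delay, and the Consent text waives the usual day-long consideration period.
- A request clock drops pre-request time from controls too, so against a presentation clock the bias can be positive, zero or negative.
- At laboratory times of 72 to 96 h, even d = 24 h leaves a gain of 46 to 71 h (m = 1 to 2 h).
- Presentation to result is already a secondary outcome, so the full-pathway comparison will be visible.

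All of this stands, and it limits the claim to what may happen. It does not remove the defect. The clinician-judgement route covers only patients without respiratory illness who fall outside the PHE case definition; the other two routes need no decision to test. A secondary outcome does not repair the primary estimate. The start event is part of the outcome definition that the protocol itself fixes, and it fixes it on a step that one group's pathway lacks.

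A fair warning also applies to the remedy. The control definition sets no limit on time from presentation to testing, so moving to a presentation clock without one could lengthen control times through late-tested inpatients and favour mPOCT. For non-hospitalised staff, whom Section 6 (Staff testing) counts in time to result, presentation has no clear meaning.

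**Conclusion.** The point holds in a limited form. The primary clock begins at an event that is natural for controls and absent from the described mPOCT pathway, so the stated definition permits asymmetric timing of the primary endpoint. If enrolment or swab is used as the mPOCT start, the difference is overstated relative to a clock that counts identification and consent, by an amount the protocol does not give. For assumed omissions of 2 to 12 h it is 2% to 55% of the apparent gain over the protocol's range of turnaround figures. The threat is mainly to effect size; the direction is in doubt only with laboratory time near 24 h and an omission near 24 h.

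This rests on assumed values of d and c, and on turnaround figures whose start points are not those of the primary outcome: the 3 to 4 days run from sampling, and the earlier-trial figures have no stated start. The mismatch with the presentation-based hypothesis and the conflict between Sections 7 and 11 need no assumption.

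**What to change.** Use one clock start in both groups, in one of two ways.

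1. Make presentation to result, now a secondary outcome, the primary. Restrict controls to patients tested within 24 h of presentation, to match the intervention eligibility limit, and exclude non-hospitalised staff from this comparison, amending the Staff testing text accordingly.
2. Keep a request clock, but define the start identically in both groups as the first recorded clinical-team decision or order to test for SARS-CoV-2, counting referral to the research team as such a decision. Enrolment and swab should never serve as the start.

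In either case, report swab to result separately as test turnaround, and correct Section 11 so that it names the same primary outcome as Section 7.

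The cost is a wording change to the primary outcome, some extra timestamp extraction, and possibly a smaller headline effect. No patients or tests are added. Option 2 assumes that a decision, order or referral time exists for every intervention patient. The comparison with laboratory PCR in Section 5 makes a parallel order plausible, but the protocol does not confirm it, so this should be checked before option 2 is chosen.
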